### **10.5 Study Results/Publication Policy**

Shire will endeavor to publish the results of all qualifying, applicable, and covered studies according to external guidelines in a timely manner regardless of whether the outcomes are perceived as positive, neutral, or negative. Additionally, Shire adheres to external guidelines (eg, Good Publication Practices 2) when forming a publication steering committee. The purpose of the publication steering committee is to act as a non-commercial body that advises or decides on dissemination of scientific study data in accordance with the scope of this policy.

All publications relating to Shire products or projects must undergo appropriate technical and intellectual property review, with Shire agreement to publish prior to release of information. The review is aimed at protecting the sponsor’s proprietary information existing either at the commencement of the study or generated during the study. To the extent permitted by the publisher and copyright law, the principal investigator will own (or share with other authors) the copyright on his/her publications. To the extent that the principal investigator has such sole, joint or shared rights, the principal investigator grants the sponsor a perpetual, irrevocable, royalty-free license to make and distribute copies of such publications.

The term “publication” refers to any public disclosure including original research articles, review articles, oral presentations, abstracts and posters at medical congresses, journal supplements, letters to the editor, invited lectures, opinion pieces, book chapters, electronic postings on medical/scientific websites, or other disclosure of the study results, in printed, electronic, oral or other form.

Subject to the terms of the paragraph below, the investigator shall have the right to publish the study results, and any background information provided by the sponsor that is necessary to include in any publication of study results, or necessary for other scholars to verify such study results. Notwithstanding the foregoing, no publication that incorporates the sponsor’s confidential information shall be submitted for publication without the sponsor’s prior written agreement to publish, and shall be given to the sponsor for review at least 60 days prior to submission for publication. If requested in writing by Shire, the institution and principal investigator shall withhold submission of such publication for up to an additional 60 days to allow for filing of a patent application.

If the study is part of a multicenter study, the first publication of the study results shall be made by the sponsor in conjunction with the sponsor's presentation of a joint, multicenter publication of the compiled and analyzed study results. If such a multicenter publication is not submitted to a journal for publication by the sponsor within an 18-month period after conclusion, abandonment, or termination of the study at all sites, or after the sponsor confirms there shall be no multicenter study publication of the study results, an investigator may individually publish the study results from the specific site in accordance with this section. The investigator must, however, acknowledge in the publication the limitations of the single-site data being presented.

Unless otherwise required by the journal in which the publication appears, or the forum in which it is made, authorship will comply with the International Committee of Medical Journal Editors (ICMJE) current standards. Participation as an investigator does not confer any rights to authorship of publications.

## 12. APPENDICES

**APPENDIX 1 PROTOCOL HISTORY**

Document	Date	Global/Country/Site Specific
Original Protocol	04 Oct 2018	Global

11.4.2.1	Incomplete Start Date.....	25
11.4.2.2	Incomplete Stop Date.....	25
11.4.3	Missing Severity Assessment for Adverse Events.....	26
11.4.4	Missing Relationship to Investigational Product for Adverse Events.....	26
11.4.5	Character Values of Clinical Laboratory Variables.....	26

12.	ANALYSIS SOFTWARE	26
13.	CHANGES TO ANALYSIS SPECIFIED IN PROTOCOL	26
14.	REFERENCES.....	27
15.	APPENDICES.....	28
15.1	Schedule of Activities	28

ABBREVIATIONS

AE	adverse event
ANOVA	analysis of variance
AUC	area under the curve
AUC _{0-∞}	area under the curve extrapolated to infinity
AUC _{0-t}	area under the curve from time 0 to the last time point of sample collection
AUC _{0-tau}	area under the curve from time 0 to the end of the dosing interval (24 hours post dose)
BLQ	below limit of quantitation
BMI	body mass index
CI	confidence interval
CL/F	total body clearance
C _{max}	maximum concentration
C _{min}	minimum concentration observed over the dosing interval
C _{trough}	Plasma concentration observed at the end of a dosing interval
CV	coefficient of variation
ECG	electrocardiogram
eCRF	electronic case report form
EM	extensive metabolizer
IM/PM	intermediate metabolizers/poor metabolizer
LLOQ	lower limit of quantification
MedDRA	Medical Dictionary for Regulatory Activities
MR	metabolite ratio
PCI	potentially clinically important
PK	pharmacokinetic(s)
PT	preferred term
Q1	25th Percentile
Q3	75th Percentile
QD	once daily
QTcB	QT interval corrected for heart rate using Bazett's formula
QTcF	QT interval corrected for heart rate using Fridericia's formula
SAP	statistical analysis plan
SD	standard deviation
SOC	system organ class
t _{1/2}	terminal half-life
TEAE	treatment-emergent adverse event
TFL	tables, figures, and listings
t _{max}	time of maximum observed concentration sampled during a dosing interval

V_z/F volume of distribution associated with the terminal slope following
extravascular administration

WHO World Health Organization

1. INTRODUCTION

This statistical analysis plan (SAP) provides a technical and detailed elaboration of the statistical analyses of pharmacokinetic (PK) and safety data described in the original study protocol dated 04 Oct 2018. Specifications for tables, figures, and listings (TFLs) are contained in a separate document (SPD422-113 TFL Shells).

2. OBJECTIVES, ESTIMANDS, AND ENDPOINTS

2.1 Objectives

2.1.1 Primary Objective

The primary objective of this study is to assess the effect of a CYP1A2 inducer (omeprazole) on the PK of anagrelide when administered concurrently.

2.1.2 Secondary Objective

The secondary objective of this study is to assess the safety and tolerability of anagrelide, omeprazole, and co-administered anagrelide plus omeprazole.

2.2 Endpoints

2.2.1 Primary Endpoints

The primary endpoints will be maximum concentration (C_{max}) and area under the curve from time 0 to the last time point of sample collection (AUC_{0-t}) and area under the curve extrapolated to infinity ($AUC_{0-\infty}$) of anagrelide and 3-hydroxyanagrelide compared between anagrelide administered alone and anagrelide administered after omeprazole 40 mg once daily (QD) for 7 days.

2.2.2 Secondary Endpoints

Safety and tolerability will be assessed throughout the study by routine recording of electrocardiograms (ECGs), vital signs, safety laboratory assessments, and adverse events (AEs).

[figure not shown]
3. STUDY DESIGN

3.1 General Description

This is a Phase 1, open-label, single-sequence, non-randomized, multiple-dose, crossover PK study to assess the effect of a CYP1A2 inducer (omeprazole 40 mg QD) on the PK of anagrelide (1 mg) when administered concurrently in healthy subjects. Up to 35 healthy

male and female subjects, aged 18 to 45 years will be screened to ensure enrollment and completion of 20 subjects. Subjects who discontinue from the study will not be replaced. The study design is shown in the study schema in [Figure 1](#).

Figure 1: Study Design Flow Chart

- SPD422 will be administered under fasting conditions on Days 1 and 8
- Omeprazole will be administered prior to breakfast on Days 2-7 and under fasting conditions on Day 8
- PK assessments for anagrelide on Day 1 and Day 8, and for omeprazole on Day 8

3.2 Randomization

Not applicable.

3.3 Blinding

Not applicable.

3.4 Sample Size and Power Considerations

Up to 35 healthy male and female subjects, aged 18 to 45 years will be screened to ensure enrollment and completion of 20 subjects. Subjects who discontinue will not be replaced.

Sample size estimation is to achieve a desired precision of the effect of interest, targeting the width of the 90% confidence interval (CI).

From a previous crossover study (SPD422-110), the within-subject coefficient variation (CV) in anagrelide log-transformed AUC was estimated to be 0.132. Allowing for a slightly larger within-subject CV of 0.15, a sample size of 11 subjects is required to estimate the mean difference between anagrelide + omeprazole and anagrelide alone in the log-transformed AUC with an error margin of at most ± 0.2231 at 90% confidence with a probability of 90%. Thus, if the true geometric mean treatment ratio is 0.6, the lower and upper 90% confidence bounds will be estimated to be within 0.48 and 0.75 ($\exp[\ln(0.6) - 0.2231]$ and $\exp[\ln(0.6) + 0.2231]$) with 90% probability. Therefore, with an overall sample size of 20 subjects, anticipated 13 to 14 CYP2C19 extensive metabolizer (EM) subjects and 6 to 7 CYP2C19 intermediate/poor metabolizer (IM/PM) subjects, this statistical power will be met for the overall population and the CYP2C19 EM population. The confidence bounds for the smaller population of CYP2C19 IM/PM subjects will be slightly wider.

4. STATISTICAL ANALYSIS SETS

4.1 Enrolled Set

The Enrolled Set consists of all subjects for whom an enrollment number has been assigned. Usually, these are the subjects who meet the study inclusion/exclusion criteria and sign the informed consent form.

4.2 Safety Set

The Safety Set consists of all subjects who have taken at least 1 dose of investigational product (anagrelide or omeprazole) and have at least 1 post-dose safety assessment.

4.3 Pharmacokinetic Set

The PK Set consists of subjects who receive at least 1 dose of investigational product (anagrelide or omeprazole) and have at least 1 measurable post-dose plasma concentration. Each subject's data (eg, dosing records, AEs, sample collection records, etc.) will be reviewed for inclusion/exclusion from the descriptive statistics and statistical analysis on a case-by-case basis at the discretion of the Pharmacokineticist.

5. STUDY SUBJECTS

5.1 Disposition of Subjects

The number of subjects who were included in each defined analysis set (Enrolled, Safety, and PK) will be summarized overall.

The number and percentage of subjects who completed the study or prematurely discontinued will be presented overall, along with primary reasons for discontinuation, as recorded on the study completion/early termination page of the electronic case report form (eCRF). All enrolled subjects who prematurely discontinued the study will be listed in the subject disposition listing along with reasons for discontinuation.

Subject disposition summary and listings will be based on the Enrolled Set.

5.2 Demographic and Other Baseline Characteristics

Descriptive summaries of demographic and baseline characteristics will be generated for the Safety Set and the PK Set.

The observed omeprazole $AUC_{0-\tau}$ will be used to define the CYP2C19 metabolizer status of subjects, with $AUC_{0-\tau} < 5,200$ ng•h/mL (< 15 μ mol/L) classified as CYP2C19 EM and $AUC_{0-\tau} \geq 5,200$ ng•h/mL (≥ 15 μ mol/L) classified as CYP2C19 IM/PM. The summaries of demographic and baseline characteristics for the PK Set will be presented by the CYP2C19 metabolizer status (EMs and IMs/PMs) and overall.

The following demographic and baseline characteristics will be summarized in the following order in the tables: age (years), sex, ethnicity, race, weight (kg), height (cm), and body mass index (BMI, kg/m²).

Continuous variables, such as age, weight, height, and BMI will be summarized using descriptive statistics including number of subjects, mean, standard deviation (SD), median, minimum, and maximum. Categorical variables such as sex, ethnicity and race will be summarized by reporting the number and percentage of subjects in each category. All summarized values will be taken from the latest available assessments at the Screening Visit.

Demographic and baseline characteristics will be listed for the Safety Set.

5.3 Medical History

Medical history will be collected at the Screening visit and will be coded using Medical Dictionary for Regulatory Activities (MedDRA) Version 21.1. A listing will be provided using the Safety Set.

Medical history will be summarized by system organ class (SOC) and preferred term (PT) for the Safety Set.

5.4 Prior Medications

Prior medications will be coded using the World Health Organization (WHO) Drug Dictionary Enhanced Version dated 01 September 2018.

Prior medication is defined as any medication with the start date prior to the date of first dose of investigational product.

Prior medication usage will be summarized by the number and proportion of subjects receiving each medication by PT and overall for the Safety Set. Multiple medication usage by a subject in the same category will be counted only once.

All prior medications will be listed for the Safety Set.

5.5 Concomitant Medications

Concomitant medications will be coded using the WHO Drug Dictionary Enhanced Version dated 01 September 2018.

Concomitant medication is defined as any medication with a start date prior to the date of the first dose of investigational product and continuing after the first dose of investigational product or with a start date between the dates of the first and last doses of investigational product, inclusive. Any medication with a start date after the date of the last dose of investigational product will not be considered a concomitant medication.

Concomitant medication usage will be summarized by the number and proportion of subjects receiving each medication by PT, by treatment group and overall, for the Safety Set. Multiple medication usage by a subject in the same category will be counted only once. Concomitant medications will be assigned to the treatment(s) with which they are concomitant. A medication is concomitant with a treatment if the subject received that medication any time between the time when that treatment was received and when the next treatment was received, or in the case of the last treatment, until the end of the

follow-up period. Therefore, a medication may be concomitant with more than one treatment.

All concomitant medications will be listed for the Safety Set.

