### 3.1.4 Follow-up

[figure not shown]
A follow up telephone call (or in-person follow-up contact at the investigator's discretion) will take place 7± 2 days following the subject's last dose of investigational product to collect information on any ongoing or new adverse events (AEs), serious adverse events (SAEs) or concomitant medications, as appropriate.

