### **5.2 Concomitant Treatment**

Concomitant treatment refers to all treatment taken between the dates of the first dose of investigational product and the end of the follow-up period, inclusive. Concomitant treatment information must be recorded on the appropriate CRF page.

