#### **6.2.2 Dosing**

After satisfying all screening and entry criteria, anagrelide and/or omeprazole will be administered to all subjects according to the following schedule:

Day 1: Anagrelide 1 mg, (administered orally as two 0.5 mg capsules) will be administered to all subjects at approximately 8:00 in the morning on Day 1. Subjects are required to fast for 10 hours prior to and until 4 hours following administration of anagrelide on Day 1.

Days 2-7: Omeprazole 40 mg (administered orally, QD) will be administered to all subjects on Days 2-7. Omeprazole will be administered at approximately 8:00 in the morning, prior to breakfast.

Day 8: Anagrelide 1 mg and omeprazole 40 mg will be administered concurrently to all subjects at approximately 8:00 in the morning on Day 8. Subjects are required to fast for 10 hours prior to and until 4 hours following administration of anagrelide and omeprazole on Day 8.

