7.1 Adverse Events

Adverse events will be coded using MedDRA Version 21.1.

An AE (classified by PT) will be considered a treatment-emergent AE (TEAE) if it starts on or after dosing on Day 1, or if it starts before dosing on Day 1 but increases in severity on or after dosing on Day 1 through the end of the study. If more than 1 AE with the same PT is reported before dosing on Day 1, then the AE with the greatest severity will be used as the benchmark for comparison to the AEs occurring after dosing on Day 1 under the PT.

Treatment most recently taken when the AE occurred will be used for the summaries:

- Any AE that started (or increased in severity) on or after the administration of anagrelide on Day 1, but before the administration of omeprazole on Day 2 will be assigned to anagrelide alone;
- Any AE that started (or increased in severity) on or after the administration of omeprazole on Day 2, but before the administration of anagrelide on Day 8 will be assigned to omeprazole alone;
- Any AE that started (or increased in severity) on or after the administration of anagrelide on Day 8 will be assigned to anagrelide with omeprazole.

An overall summary of the number of subjects with TEAEs as well as the number of events will be presented by treatment group, including the number and percentage of subjects with any TEAEs, serious TEAEs, TEAEs related to investigational product, serious TEAEs related to investigational product, TEAEs leading to discontinuation of investigational product, serious TEAEs leading to discontinuation of investigational product, TEAEs leading to discontinuation from study, serious TEAEs leading to discontinuation from study, severe TEAEs, TEAEs leading to hospitalization, and TEAEs leading to death.

The number and percentage of subjects reporting TEAEs, as well as the number of events, in each treatment group and overall will be tabulated by SOC and PT, and by SOC, PT, and maximum severity. The TEAEs considered related to investigational product will also be summarized by SOC and PT. If more than 1 AE occurs with the same PT, after the same treatment for the same subject, then the subject will be counted only once for that treatment group and PT using the most severe and most related occurrence for the summarization by severity and by relationship to investigational product. Summaries by SOC and PT will present SOC sorted alphabetically and PT within SOC by descending incidence.

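### SAP 5.5 excludes medications started after each subject's last dose, although Protocol 5.2 counts them to the end of follow-up, so they reach no planned medication table or listing

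*SAP*

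**What the plan says.** Protocol 5.2 defines concomitant treatment as "all treatment taken between the dates of the first dose of investigational product and the end of the follow-up period, inclusive". Protocol 3.1.4 and 7.1.3 have the follow-up contact collect concomitant medications, and the schedule in SAP Section 15.1 marks them on Day 9 and at follow-up.

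SAP 5.5 uses a narrower definition. A medication qualifies if it began before the first dose and continued past it, or if its start date lies from the first-dose date to the last-dose date. The section then adds: "Any medication with a start date after the date of the last dose of investigational product will not be considered a concomitant medication". Two sentences later it assigns medications to treatments, and the last treatment's window runs "in the case of the last treatment, until the end of the" follow-up period.

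SAP 5.4 defines prior medications as those started before the first dose. SAP 5.4 and 5.5 provide summaries and listings for these two categories only. The concomitant summary is presented by treatment group and overall, for the Safety Set.

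For adverse events, SAP 7.1 has no cut-off at the last dose. An event that starts "on or after the administration of anagrelide on Day 8 will be assigned to anagrelide with omeprazole".

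**The concern.** The two documents define the same term differently, and medications started between the last dose and the follow-up contact fall into the gap. They are collected, but no planned table or listing contains them.

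The medication and adverse event tables then cover different periods. Suppose a completer has a headache on Day 9 and starts a medication for it that day. The headache is tabulated under the combination and the medication is not tabulated at all. Safety and tolerability of each treatment, including the combination, is the secondary objective, and a reader would expect the two tables to match.

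**Working it through.** The plan states no figure for this point. The check sets the definitions side by side and works out the dates.

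**Inputs**
- A completer's last dose is on Day 8: "Anagrelide 1 mg and omeprazole 40 mg will be administered concurrently to all subjects at approximately 8:00 in the morning on Day 8" (Protocol 6.2.2).
- The follow-up contact is 7 ± 2 "days following the subject's last dose of investigational product to collect information on any ongoing or new adverse events" (Protocol 3.1.4). It therefore falls 5 to 9 days after the last dose.
- The SAP cut-off is the subject's own last-dose date, D (SAP 5.5).
- The Safety Set needs one dose of either product and one post-dose safety assessment (SAP 4.2). Discontinued subjects are followed up where possible (Protocol 4.5).

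**One medication under each rule: a completer first takes it on Day 10**
- Protocol 5.2: concomitant.
- SAP 5.5, definition and exclusion sentence: not concomitant.
- SAP 5.5, assignment rule taken alone: belongs to the combination.
- SAP 5.4: not prior.
- SAP 7.1, for an adverse event starting the same day: assigned to the combination.

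**Excluded start dates**

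Formula: from D + 1 to the contact at D + 5 to D + 9, which is 5 to 9 days (nominally 7).

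| Subject | D | Contact | Excluded starts | Column affected |
|---|---|---|---|---|
| Completer | 8 | 8 + 5 = 13 to 8 + 9 = 17 | Day 9 to Day 13-17 | combination |
| Stops after Day 1 | 1 | 1 + 5 = 6 to 1 + 9 = 10 | Day 2 to Day 6-10 | anagrelide alone |
| Stops after Day 5 | 5 | 5 + 5 = 10 to 5 + 9 = 14 | Day 6 to Day 10-14 | omeprazole alone |

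The overall column loses the same medications in every row.

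**Completers in hours, with dosing at about 08:00**
- Anagrelide alone: Day 1 to Day 2, 24 h, nothing cut.
- Omeprazole alone: Day 2 to Day 8, 6 × 24 = 144 h, nothing cut.
- Combination, new starts only: 08:00 to midnight on Day 8, 16 h, against 5 × 24 = 120 h to 9 × 24 = 216 h under the follow-up rule.

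Medications already started by Day 8 and continuing still count under the combination.

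**The case against.** The strongest reply is that SAP 5.5 first decides which medications qualify and then assigns the qualifying ones to treatments. On that reading the follow-up clause only carries forward medications already started by the last dose. For example, a medication taken from Day 5 to Day 12 counts under omeprazole alone and under the combination. This is coherent, so a reader who infers that the two SAP sentences cannot both apply goes further than the text. It leaves the follow-up clause with little to do, however, and it does not touch the difference from Protocol 5.2.

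A reader might also infer an undeclared change of analysis, because SAP Section 13 reports none. That is weak. Protocol 5.2 sits with the recording requirements, and Protocol 9.4 leaves the approach to summarizing medications to the SAP. The mismatch is one of definition.

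Three stronger readings of the size also fail:
- *Only the combination is undercounted.* This is true for completers. For others the cut-off follows the subject's own last dose, so early stoppers lose medications from another column.
- *Almost the whole combination window is lost.* This applies to new starts only.
- *Each omitted user is worth 1/20 = 5 percentage points.* This requires 20 subjects in the column and no earlier qualifying use of the same preferred term by that subject under that treatment.

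It is also fair to say that the number may be small. Exclusion criterion 4 bars medication through Day 9, apart from occasional acetaminophen, and Protocol 5.2.1 asks subjects to refrain during the study. Protocol 5.2.1 also requires every medication to be recorded on the CRF, so no data are lost.

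**Conclusion.** The point holds, at low severity. The SAP states a rule that produces a table at odds with the protocol's definition, and it leaves medications first started after the last dose in no planned summary or listing. Adverse events from the same days are attributed to the last treatment.

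The affected start dates span 5 to 9 days after each subject's last dose. The number of medications or users omitted cannot be derived, since the documents give neither a medication-use rate nor a dropout rate.

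The date ranges assume that follow-up is timed from the last dose of investigational product, as in Protocol 3.1.4. The schedule footnote counts from the last anagrelide dose. That is the same day for completers but gives an earlier contact for a subject who stops on Days 2-7.

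Only descriptive medication output is affected. The rule governs tabulation, so the pharmacokinetic comparison and the adverse event tables do not change.

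**What to change.** Make two edits in SAP 5.5:
1. Delete the sentence that excludes medications started after the last dose.
2. In the definition, replace the span from first to last dose with the span from the first dose to the end of the follow-up period, as in Protocol 5.2. Deleting the sentence alone is not enough, because the definition would still stop at the last dose.

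Keep the existing assignment rule, which then works as written.

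The medications are already collected, so no new data are needed. The small downside is that the last treatment's column covers a longer, mostly off-drug window: for completers, Day 8 to Day 13-17, against one day for anagrelide alone and six for omeprazole alone. Flagging starts after the last dose in the listing lets a reader separate them.
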